## LIST OF ABBREVIATIONS

CO	Carbon Monoxide
DSMB	Data and Safety Monitoring Board
EMA	Ecological Momentary Assessment
ENDS	Electronic Nicotine Delivery Systems
EVALI	E-cigarette, or Vaping, Product Use Associated Lung Injury
FDA	Food and Drug Administration
ITP	Investigational Tobacco Product
IRB	Institutional Review Board
NIDA	National Institute of Drug Abuse
OPRS	Office for the Protection of Research Subjects
PI	Principal Investigator
REDCap	Research Electronic Data Capture
SAE	Serious Adverse Event
SBIR	Small Business Innovation Research
SREC	Standardized Research E-Cigarette
UIC	University of Illinois at Chicago

## 1.0 Project Summary/Abstract

Combustible tobacco use remains the primary cause of cancer morbidity and mortality in the United States, and a major cause of cardiovascular and pulmonary diseases. Although there has been tremendous progress in reducing cigarette smoking, approximately 15% of adults over age 18 in the U.S. currently smoke cigarettes, and progress with smoking cessation appears to be stalling. To reduce the substantial toll from cigarette smoking, we need to consider a variety of approaches to more rapidly reduce its harm, especially for smokers who are not motivated or ready to stop smoking or who have been unsuccessful in quitting with current cessation treatments. The primary purpose of this study is to examine whether conventional, combustible cigarette smokers can reduce their use of cigarettes and associated harms by switching to an e-cigarette (Standardized Research E-Cigarette or SREC). This project will use Ecological Momentary Assessments (EMA) to gather real-time, naturalistic reports of conventional smokers' use and experience of a SREC as they attempt to switch from combustible cigarettes to SREC. We will examine how the proximal contexts and subjective experiences surrounding SREC use differ from smokers' patterns and responses to conventional cigarette use, and how these differences may predict success in switching. In addition, we will assess in-depth, in real time, smokers' reports of urges and withdrawal symptoms as they switch to a SREC. We will also evaluate changes in health and biomarker variables. We will enroll a sample of 120 adult combustible cigarette smokers who are interested in switching to an e-cigarette. Participants will complete a baseline one-week EMA wave while they are smoking their usual cigarettes, complete baseline assessments, and then will be randomized (within sex) in a 1:1 ratio to either usual flavor SREC pods or free choice of flavors SREC pods. Participants in the usual flavor condition will receive either tobacco (regular smokers) or menthol (menthol smokers) while those in the free choice condition can choose from the following flavors: tobacco, menthol, watermelon, and blueberry. Participants will receive brief behavioral counseling about reducing cigarettes and switching to the SREC. After one week of using a SREC, they will complete another EMA week to assess patterns and responses to use of both the SREC and cigarettes. Participants will receive 12 weeks of SREC supplies; complete daily reports of product use along with bi-weekly check-ins through the end of the 12-week trial, and then complete a one-month follow-up. Our aims are to: 1) Examine whether conventional cigarette smokers can significantly reduce their combustible cigarette use by switching to SREC; 2) Examine whether reductions in conventional cigarette use and uptake of SREC are associated with changes in health and biomarker variables; 3) Examine smokers' subjective responses to SREC in real time, as they are used, and whether these responses are associated with cigarette reduction; and 4) Examine how patterns of use (e.g., contexts, timing) and subjective experience with SREC differ from conventional cigarette use, and whether differences are associated with success in switching to SREC. Data from this study will provide valuable information about the potential for harm reduction if cigarette smokers switch to a SREC.

## 2.0 Background/Scientific Rationale

Combustible tobacco use remains the primary cause of cancer morbidity and mortality in the United States, and a major cause of cardiovascular and pulmonary diseases. Although there has been tremendous progress in reducing smoking, 15% of adults in the U.S. currently smoke cigarettes. To reduce the substantial toll from tobacco, we need to consider a variety of approaches to more rapidly reduce its harm, especially for those smokers who may not be motivated to stop smoking or who have been unsuccessful in quitting. The primary purpose of this study is to examine whether combustible cigarette smokers can reduce their use of cigarettes and associated harms by switching to a SREC. Smokers continue to smoke primarily because of the nicotine. Yet most of the morbidity and mortality associated with cigarette smoking comes not from the nicotine, but rather, from a variety of toxins and constituents that result from the combustion process. E-cigarettes or Electronic Nicotine Delivery Systems (ENDS) may provide an alternative way for smokers who are unable to quit, or who are not motivated to quit, to address their nicotine addiction without many of the harms associated with the combustion process. ENDS use in the U.S. has increased dramatically over the past several years, and in 2014, approximately 20.3% of current cigarette smokers reported using e-cigarettes. Among those who had tried to quit smoking in the past year, more than half reported using an e-cigarette to help them quit. Given this increasing use and potential appeal of ENDS among current smokers, there is an imperative need to understand better its potential benefits or harms. However, research to date has been limited by the large variety of ENDS products and the lack of comparability across studies. With the advent of a

SREC, we can now better address several critical questions about potential benefits for smokers who switch to an e-cigarette.

ENDS attempt to duplicate the sensory and behavioral characteristics of cigarettes. Users inhale a nicotine-containing vapor that is partially absorbed through the pulmonary system. Although nicotine itself presents little cardiovascular risk and is not a carcinogen, other ingredients besides nicotine are inhaled, and there is the possibility of harm from some of these ingredients. E-cigarette vapor contains particulate matter, but the level of toxicity and health effects from these particulates is not yet clear. Frequent exposure to fine and ultrafine particles from tobacco smoke can contribute to pulmonary and inflammatory processes, which in turn, can increase the risk for cardiovascular and respiratory diseases. It is not yet known definitely whether the particles delivered by e-cigarettes have the same health effects as the particles generated by conventional cigarette smoke, and there is some suggestion that the amount of particle matter may vary by nicotine content. Some researchers have estimated that e-cigarette aerosol would result in only about 25% of particles being deposited into the circulatory system and organs, far lower than that of conventional cigarette smoking. E-cigarette aerosol may also contain a variety of metals (e.g., tin, nickel, lead, copper, chromium), some of which may come from the heating elements, and which could also be deposited in the lungs and cause respiratory toxicity. Overall, though, the evidence to date suggests that although e-cigarette aerosol may contain some toxicants, these are at markedly lower levels than found with tobacco smoke, and that there are negligible levels of carcinogens.

Only a few studies have examined the health effects of exposure to e-cigarette aerosol, and the biological effects are mixed. Some studies, for example, have found that acute puffing on e-cigarettes does not affect pulmonary function or inflammatory markers, but that it may constrict airways. Most studies of the health effects of e-cigarettes have assessed acute or very short-term exposure effects with relatively small sample sizes, and there is extremely limited data on health effects assessed from e-cigarettes as they are actually used. E-cigarette aerosol may have biological effects, but we need to know more about these effects as smokers actually use the products and whether there are reductions in harm relative to smokers' use of conventional cigarettes. In a recent review of the safety of e-cigarettes, Farsalinos and Polosa concluded that the clinical studies that have evaluated the effects of short-term e-cigarette use on cardiovascular and respiratory functional outcomes have shown that even if some harmful effects are reported, these effects are significantly milder than those derived from smoking conventional cigarettes. Dinakar and O'Connor reached a similar conclusion and further noted that the diversity of e-cigarette products has made it challenging to reach consensus about their safety and efficacy. For example, the sudden outbreak of pulmonary illnesses in Fall 2019 that are known as e-cigarette or vaping associated lung injuries (EVALI) appears to be associated with vaping e-liquids that contain THC, and/or using devices or liquids that were purchased or mixed off market (e.g., off the streets or from friends and family, not from licensed retailers). The SREC device used in this study does not contain THC and comes from a NIDA-funded SBIR contract for a standardized e-cigarette to NJOY LLC (a requirement for grants funded under this Program Announcement).

## **2.1. E-cigarettes and Smoking Reduction and Cessation**

Currently there is little consensus about whether e-cigarettes aid in smoking cessation or reduction. Several studies have found reductions in cigarettes per day among adult smokers who use e-cigarettes. The value of the reduction is likely to depend, though, on the level achieved and perhaps whether it represents a path to cessation, given that reducing the number of cigarettes smoked per day will have smaller health benefits than quitting completely. For cardiovascular disease, even very light smoking (less than 5 cigarettes/day) is associated with a notable increase in risk for disease. A recent systematic review and meta-analysis by Kalkhoran and Glantz concluded that e-cigarettes were associated with less quitting among current smokers. However, there have been substantial criticisms about the methods of this review and inclusion criteria. Another recent comprehensive systematic review concluded that a majority of studies show a positive association between e-cigarette use and smoking cessation. These authors also note, though, that this research is still in its infancy, with few well-designed studies, and at this point, there is not a strong body of evidence to draw any firm conclusions. Malas et al. further conclude that we need randomized controlled clinical trials outside of lab settings and that can provide insight into contextual and behavioral mechanisms. They also note that the effectiveness of e-cigarettes to "reduce withdrawal symptoms and cravings in real-life settings remains uncertain" (p.9).

## 2.2. Ecological Momentary Assessments (EMA)

EMA provides an excellent window into the lives of tobacco users and a way to examine specific hypotheses about subjective experiences with combustibles and e-cigarettes, and the moderating effects of contexts. It is an excellent vehicle to address the questions about contextual and behavioral mechanisms that Malas et al. suggest are needed. EMA involves repeated sampling of individuals' behavior and experiences in real time in the natural environments in which they occur. EMA maximizes ecological validity, minimizes recall bias, and allows for examining micro-contexts that influence behavior. EMA captures subtle variations in mood as they occur and can do so more accurately than other measurement modalities.

EMA has many advantages over other methods for examining subjective experiences and other influences on tobacco use behaviors. First, EMA is well suited for measuring intra-individual variability and small shifts in mood that may play a role in cueing the use of cigarettes or e-cigarettes. In addition, with the use of random assessments independent from the occurrence of specific events, EMA provides useful comparison information about background moods, urges, and withdrawal symptoms. Second, EMA data allow us to separate between-subject vs. within-subject effects. We have described mixed model approaches incorporating a log-linear structure for determinants of within-subject variances using EMA data and have extended this approach to modeling between-subject variances. As illustrated by Hedeker et al., these approaches are useful in the simultaneous consideration of both between- and within-subject effects. These models allow for the simultaneous testing of hypotheses about whether subjective responses to tobacco use vary by smoking pattern or level (between-subjects effect), as well as whether mood varies with combustible and ENDS use (within-subjects effect). Third, EMA provides the opportunity to examine individual variability (variance) that may enhance our ability to predict changes in tobacco use patterns above and beyond mean information alone. Our work has shown the feasibility of EMA for examining moods, tobacco use, and contexts among adolescents, young adults, and dual-using smokers (those who use both cigarettes and ENDS).

## 3.0. Objectives/Aims

This project will use EMA to gather real-time reports of smokers' use and experience of SREC as they switch from combustible cigarettes to SREC. We will examine how the proximal contexts and subjective experiences of SREC use differ from smokers' patterns and responses to usual cigarette use, and how these patterns predict switching success. We will examine whether increasing flavor choice will improve adherence to e-cigarettes and so increase the degree of switching. We will assess in real time, smokers' reports of urges and withdrawal symptoms as they switch to SREC. We will also evaluate changes in health and biomarker variables. We will enroll a sample of 120 adult (age 21 and older) cigarette smokers who are interested in reducing their cigarette use by switching to e-cigarettes. Participants will complete baseline assessments and a one-week EMA wave while they are smoking their usual cigarettes, and then will be randomized in a 1:1 ratio to either their usual flavor SREC pods or free choice of flavored SREC pods. Participants in the usual flavor condition will receive either tobacco (regular smokers) or menthol (menthol smokers) while those in the free choice condition can choose from the following SREC flavors: tobacco, menthol, watermelon, and blueberry. Participants in the flavor choice condition will be able to select from these flavors throughout the trial based on their preference. All participants will receive brief behavioral counseling about reducing their cigarette use and switching to the SREC. After an initial week of using SREC, they will complete another EMA week assessing patterns and responses to use of products. Participants will receive 12 weeks of SREC pods; complete daily reports of product use along with bi-weekly check-ins through the end of the 12-week trial, and then complete a one-month follow-up. The total study duration for participants is 18 weeks. **We will address the following specific aims:**

**AIM 1: Examine whether conventional cigarette smokers can significantly reduce their combustible cigarette use by switching to SREC.** We hypothesize that smokers randomized to the flavor choice condition will show significantly greater reductions in combustible cigarette use than smokers in the usual flavor condition. We will assess changes in use of products over a 12-week trial. We will also examine moderators of effects, including sex, baseline menthol cigarette use (not SREC flavor), and nicotine dependence level at baseline.

**AIM 2: Examine whether reductions in conventional cigarette use and uptake of SREC are associated with changes in health and biomarker variables.** We will have longitudinal measures of all

combustible tobacco products as well as SREC use and will examine how these longitudinal changes in patterns of use are associated with changes in expired air carbon monoxide (CO); blood pressure; heart rate; weight; respiratory symptoms; withdrawal symptoms; and nicotine dependence. We hypothesize that smokers who show more complete substitution will show greater reductions in CO and respiratory symptoms.

**AIM 3: Examine smokers' subjective responses to SREC in real time, as they are used, and whether these responses are associated with cigarette reduction.** We hypothesize that smokers in the flavor choice condition will show more adherence to the switching intervention and report higher levels of satisfaction, pleasure, and mood enhancements than smokers in the usual flavor EC condition and that these responses will predict level of cigarette reduction. Data will come from EMA measures and daily surveys. We will also descriptively examine how SREC flavor may be associated with subjective responses.

**AIM 4: Examine how patterns of use (e.g., contexts, timing) and subjective experience with SREC differ from conventional cigarette use, and whether differences are associated with success in switching to SREC.** These within-subject analyses will use EMA data. We hypothesize that subjects who have fewer differences in patterns and experiences between cigarettes and SREC will reduce cigarettes more and maintain SREC use longer.

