**Table 1: Timeline of Assessments and Procedures**

Week	Procedures	Modality	Visit Duration (in minutes)
0	Screening eligibility	On-line and phone	
1	CO; pregnancy test; baseline questionnaires on tablet (if not already completed); vital signs; height and weight; EMA training; go home with EMA and smoke usual cigarettes	In-person visit	90-120
2	De-brief EMA; CO; Counseling about reduction and switch; brief questionnaire; given week supply of SREC; daily reports of use	In-person visit; daily text/web reports of use	60
3	Return used pods; CO; Brief counseling to problem solve reduction and switch; given new week supply of SREC; start EMA	In-person visit; daily text/web reports	40
4	Debrief EMA week; return used pods; CO; brief review of progress and problem-solve; given 2-week supply of SREC	In-person visit; daily text/web reports of use	40
5	Daily reports of use via text/web	Daily Text/web reports of use	
6	Brief check-in to give next 2-week supply of SREC; return used pods; CO; continue daily reports of use via text/web; pregnancy test	In-person visit; daily text/web reports of use	20
7	Daily reports of use via text/web	Daily Text/web reports of use	
8	Brief check-in to return used pods; given next 2-week SREC supply; CO; continue daily reports of use via text/web	In-person visit; daily text/web reports of use	20
9	Daily reports of use via text/web	Daily Text/web reports of use	
10	Daily reports of use via text/web	Daily text/web reports of use	
11	Brief check-in to return used pods; CO; given next supply of SREC; continue daily reports of use via text/web; pregnancy test	In-person visit; daily Text/web reports of use	20
12	Daily reports of use via text/web	Daily text/web reports of use	
13	Daily reports of use via text/web	Daily Text/web reports of use	
14	End-of-treatment full assessment battery; CO; vitals; height and weight; collect SREC device and remaining pods; daily reports of use surveys end	In-person	60
18	Brief follow-up about cigarette and ENDS use over past month	Web/phone based	15

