### **6.3. Surveys**

We will collect data via several different processes: 1) Online/In-person assessments (questionnaires and physiological markers; vital signs); 2) Automated email prompts providing web or text-based links for participants to report cigarette and SREC use at the end of each day; 3) EMA app during two separate 7-day periods (weeks 1 and 3); and 4) web or phone-based questionnaire for the one-month follow-up. All participants in both conditions receive all assessments.

Table 2 presents the timeline of the constructs assessed. Proposed measures for the questionnaires are based on established scales/measures and were selected to harmonize with ongoing national surveys (e.g., PATH- Population Assessment of Population and Health Study). All measures will be ones with good

psychometric properties and that we have used in prior research and may be modified based on need to harmonize with other SREC studies.

Table 2: Assessments	Week Number															
	1	2	3	4	5	6	7	8	9	10	11	12	13	14	18	
Demographics	x															
Medical History/Perceived Health	x															
Respiratory Symptom Q's (SGRQ) 	x													x	x	
Body Weight and Height	x													x		
Vital Signs: e.g., BP, heart rate	x	x	x	X		x		x			x			x		
Smoking and total tobacco use history (all forms combustible and non); patterns and quit attempts; prior cessation medication use	x															
Nicotine dependence: FTND  , WISDM 	x													x		
Breath CO	x	x	x	X		x		x			x			x		
Pregnancy test (female only)	x					x					x					
Withdrawal symptoms (Minnesota Nicotine Withdrawal Scale; Wisconsin Withdrawal Scale  )	x	x	x	X		x		x			x			x	x	
Craving and urges (QSU-brief) 	x	x	x	X		x		x			x			x		
Satisfaction/Pleasure with cigarettes/e-cigs; Subjective experience; appeal 	x	x	x	X		x		x			x			x		
Motivation to reduce and to quit smoking (rating scale)	x													x	x	
Motivations to use E-cigs	x													x		
E-cig Expectancies	x													x		
Intentions to use E-cigs	x	x	x	X	x	x	x	x	x	x	x	x	x	x	x	
Confidence to reduce cigarettes and quit (rating scale)	x													x		
Tobacco use in social network/household	x													x		
Social support for reduction/quitting	x													x		
Mood: PANAS 	x													x		
Alcohol, Marijuana and Substance Use	x													x		
Adherence/Use of SREC			x	X	x	x	x	x	x	x	x	x	x	x		
Daily Use of Cigarettes/SREC	x	x	x	X	x	x	x	x	x	x	x	x	x	x	x	

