Adverse Events (e.g., throat irritation, nausea)			x	X	x	x	x	x	x	x	x	x	x	x		

A. A **Comprehensive questionnaire** (baseline and 14-Week End of Treatment visits) will be completed in-person to assess key constructs [e.g., sociodemographics, tobacco and nicotine use (history, dependence, attitudes, motivations, intentions, perceived harm), tobacco environment, cessation history and intentions, and other substance use]. Each questionnaire will take approximately 30 - 40 minutes to complete. Shorter **brief surveys** (5-7 minutes to complete) will be completed at weeks 2, 3, 4, 6, 8, and 11. These measures serve as important descriptors of our sample, serve as covariates or moderators in our analyses, and serve as predictors of success in reducing cigarettes and switching to SREC over time.

B. A **daily use survey** completed online via REDCap from an emailed or texted survey link starting at the week 2 visit through the week 14 visit (over the 12 treatment weeks) to assess the use of cigarettes, SREC, and any other e-cigarette/nicotine vaporizer. Each of these surveys will take about 1 minute to complete. This brief survey will serve as an indicator of change in patterns of use as well as a way for the Clinical Interviewer Staff to track progress with cigarette reduction and to monitor nicotine exposure during the treatment phase. Daily surveys ask about the number of cigarettes smoked and the number of SREC or other e-cigarette episodes on the previous day (an episode is defined as 15 puffs or a period lasting about 10 mins). We also ask if the participant finished a pod on the previous day.

C. **Two, week-long waves of EMA data collection** using a **study provided smartphone**, the first wave will take place immediately following completion of the baseline questionnaire (week 1 visit through week 2 visit), and the second wave will take place starting at the week 3 visit through the week 4 visit. The first week of EMA provides the baseline comparison with combustible cigarettes to the second EMA wave when participants will have one week of experience with using the SREC and some practice cutting down on their cigarette smoking. Each EMA wave will cover 7 consecutive days, ensuring both weekday and weekend sampling.

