We will provide a study smartphone with the custom app installed to each participant. The app is specifically developed for the EMA data collection, which will conduct brief tobacco use interviews through random prompts and participant-initiated recordings of cigarette/SREC/e-cigarette use episodes. The EMA app will “beep” randomly between 5 -7 times a day during waking hours, and ask questions about the participant's daily experiences, such as what they are doing, who they are with, and how they are feeling. It will also ask about cigarette/SREC/e-cigarette use and use of alcohol and marijuana. These interviews will take about two minutes each to complete. Participants also initiate an interview on the app each time they smoke a cigarette or use the SREC device (or other e-cigarette/vaporizer). Each of these interviews also take about 3 minutes to complete. When participants event-record cigarette/SREC use, they respond to questions about their immediate context and mood, but also answer questions related to their cigarette/SREC use. First, they will indicate which product they are using, and subsequent questions are tailored to that product. They will be asked about quantity (e.g., how many cigarettes, how many puffs), how much they wanted to use that specific product, how strong their urge was to smoke (asked regardless of product used), how much they “craved” a cigarette (asked regardless of product used), and potential withdrawal and nicotine-related symptoms (restless, impatient, hungry, sick, buzzed). They will also be asked about “throat hit” and any throat irritation. Other withdrawal symptoms are already included in our mood assessments (e.g., irritable, trouble concentrating, anxious). We will train participants individually on how to use the app. Given the ubiquity of smartphones, participants rarely have difficulty completing prompts. After the first day, the trainer will call participants to assess compliance and assist with problems. Research staff will be available via phone and email throughout the week to respond to research or technology issues with the phone or app.

D. **Semi-structured, debriefing interview** (see Appendix: ED Debriefing Interview) following each wave of EMA data collection this interview will be conducted to assess compliance with the EMA protocol, reactivity to carrying the ED, a review of data quality, and obtain feedback on the EMA data collection experience. The debriefing interview will take about 20 minutes.

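### Aim 2 promises repeated measures of all combustible tobacco, but no repeated post-baseline item covers smoked tobacco other than cigarettes, so changes in other smoked products could distort the link between cigarette reduction and CO unseen

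*Combined protocol and SAP*

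**What the plan says.** Section 3.0, Aim 2, promises repeated measures of every smoked tobacco product, referring to "combustible tobacco products as well as SREC use and will examine how these longitudinal changes in patterns of use are associated"; the outcomes it lists are CO, blood pressure, heart rate, weight, respiratory symptoms, withdrawal and dependence. It hypothesizes that more complete substitution brings larger falls in CO and respiratory symptoms.

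Section 6.3 describes what is collected:

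- In Table 2 the only row spanning all tobacco forms, "Smoking and total tobacco use history (all forms combustible and non); patterns and quit attempts; prior cessation medication use", is marked at week 1 alone.
- The repeated row is "Daily Use of Cigarettes/SREC".
- The daily survey, from the week 2 visit to the week 14 visit, is "to assess the use of cigarettes, SREC, and any other e-cigarette/nicotine vaporizer". Its counts are described as follows: "Daily surveys ask about the number of cigarettes smoked and the number of SREC or other e-cigarette episodes on the previous day".
- Participants start an EMA report when they smoke a cigarette or use the SREC or another vaping device. Of the random EMA prompts the section says: "It will also ask about cigarette/SREC/e-cigarette use and use of alcohol and marijuana".
- Alcohol, marijuana and other substance use has a Table 2 row at weeks 1 and 14. The week 14 comprehensive questionnaire also has a tobacco and nicotine section, without a list of products.

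In Table 1 the week 18 contact is a "Brief follow-up about cigarette and ENDS use over past month".

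Section 9.0, Aim 2, takes as exposure the weekly cigarette count and SREC use (episodes or weight of returned pods). It names no term for other smoked products. Section 6.1 says participants are instructed to avoid other tobacco and nicotine products while in the study.

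**The concern.** CO is raised by any smoked product, not only by cigarettes. Aim 2 asks whether people who cut cigarettes further show larger falls in CO. To read that association as the plan intends, the analyst must know whether other smoking changed as well. The aim's wording says this will be known, but the measurement schedule and the model show that it will not.

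The error could run in either direction. A participant who replaces cigarettes with little cigars shows a large fall in cigarettes and little fall in CO, which weakens the association. A participant who drops both together shows a larger CO fall than the cigarette count explains, which strengthens it. Neither case could be recognized from the repeated data, and use not asked about during follow-up cannot be reliably reconstructed later.

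**Working it through.** **1. Coverage against the CO schedule.** Table 2 marks breath CO at weeks 1, 2, 3, 4, 6, 8, 11 and 14.

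| Product | Where recorded | In the Aim 2 model? |
|---|---|---|
| Cigarettes | Daily survey, week 2 to week 14 visit; EMA in weeks 1 and 3; week 18 | Yes |
| SREC | Daily survey; EMA; returned pods | Yes |
| Other e-cigarettes | Daily survey; EMA; week 18 (ENDS) | Not named |
| Cigars, little cigars, pipes, other smoked tobacco | Week 1 item on all forms; possibly the week 14 tobacco section, coverage unstated | No |
| Marijuana | EMA in weeks 1 and 3; questionnaires at weeks 1 and 14; mode of use unstated | No |

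For other smoked tobacco there is one certain measurement and at most two, against eight CO readings. For marijuana, the CO readings at weeks 6, 8 and 11 have no accompanying item. CO is not taken at week 18, so the narrow week 18 survey does not affect the CO model.

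**2. Is the gap closed elsewhere?** The eligibility criteria exclude daily ENDS users but say nothing about cigars, pipes or cannabis. The instruction in section 6.1 covers tobacco and nicotine, does not name cannabis, and has no described compliance check for other combustibles. By contrast, participants must also agree to avoid other e-cigarettes, and those are still asked about every day.

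**3. The plan's own Aim 2 figure.** Section 12.0 gives a detectable correlation of 0.262 with 108 participants, power 0.8, two-tailed. Alpha is not stated in that sentence; 0.05 is assumed here. With a noncentral t distribution on n − 2 = 106 degrees of freedom:

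noncentrality = r√n / √(1 − r²) = 0.262 × √108 / √(1 − 0.262²) = 0.262 × 10.392 / 0.965 = 2.82

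This gives power 0.798, and the correlation detectable at 0.80 is 0.2625. Fisher's z gives 0.267, and power 0.785 at 0.262. The stated figure reproduces, with no spare margin.

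**4. Scale, by assumption only.** The documents give no rate of other smoked-product use. Suppose recorded cigarette change measures change in all smoked tobacco with reliability R and classical error, and suppose the true correlation is 0.262. The observed correlation is then 0.262 × √R:

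| R | Observed r | Power at n = 108 | n for power 0.80 |
|---|---|---|---|
| 1.00 | 0.262 | 0.80 | 109 |
| 0.95 | 0.255 | 0.78 | 115 |
| 0.90 | 0.249 | 0.75 | 122 |
| 0.80 | 0.234 | 0.70 | 138 |
| 0.70 | 0.219 | 0.64 | 158 |

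R is not known. If changes in other smoking are related to cigarette reduction, the error is not classical and this table does not apply. It shows how sensitive the calculation is and is not an estimate for this trial.

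**The case against.** The strongest reply is that this is a mismatch of wording in a secondary aim and that the plan has several protections. Much of that is fair.

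- A reader might infer that nothing but cigarettes and e-cigarettes is recorded after baseline. The documents do not support this: marijuana is asked in the week 3 EMA wave and at week 14, and the week 14 tobacco section may cover other products. Section 6.3 also says questionnaire measures serve as covariates or moderators, although section 9.0 names none of this kind for Aim 2.
- A reader might infer that moving to cigars counts as successful switching and misclassifies the primary outcome. It does not. The primary endpoint is combustible cigarettes per day, and a person who smokes fewer cigarettes has reduced on that measure. Abstinence also requires CO below 3 ppm, so recent users of other smoked products would tend to be classed as not abstinent.
- A reader might infer a bias that differs by arm, with usual-flavor participants turning to other smoked products. Nothing in the documents supports or excludes this.
- A reader might attach a definite power loss. For example, if 10–15% of participants had CO unrelated to cigarette change, r would be 0.262 × 0.90 = 0.236 to 0.262 × 0.85 = 0.223, with Fisher z power of about 0.69 to 0.64. That requires CO to be wholly independent of cigarette change in those people. A steady user of another product adds a roughly constant amount of CO, so change in CO still follows cigarettes. Only changes in other use matter. Moreover, 0.262 is a detectability threshold framed around SREC change and health outcomes generally, not an expected cigarette–CO correlation.
- Cannabis lies outside Aim 2's promise, which concerns tobacco. It belongs here only as another source of CO.

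The instruction to avoid other tobacco lowers the risk. It does not show whether participants followed it, and it does not supply the exposure that Aim 2 says will be available.

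**Conclusion.** The concern stands as a conflict between an aim and its instruments. Aim 2's stated exposure, all combustible tobacco over time, cannot be built from the data described. The Aim 2 model covers cigarettes and SREC only. A change in other smoked products would alter CO without being recorded at most CO visits and could bias the association between cigarette reduction and CO in either direction.

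The size is unknown; the figures in step 4 rest on assumed reliabilities. The conclusion assumes that some participants change their use of other smoked products during follow-up, and that the week 14 tobacco section, whatever it covers, is a single time point. It does not reach the primary endpoint. The remedy is inexpensive and should be adopted if data collection allows.

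**What to change.** Add one or two items to the daily survey, or at least to each visit's brief survey: the amount of cigars, little cigars, pipe or other smoked tobacco since the last report, and any smoked cannabis. In section 9.0, enter these as time-varying covariates in the Aim 2 CO model. Repeat the analysis with total combusted tobacco as the exposure, as a sensitivity analysis, and define in advance how products are added together. State which products the week 14 tobacco section covers.

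If the items are not added, narrow the Aim 2 wording to cigarettes and report unmeasured smoking of other products as a limitation of the CO results.

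The cost is a few seconds of extra response time in an existing REDCap survey and one extra analysis. The sample size and the primary analysis do not change.
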